2. STUDY OBJECTIVES

2.1 Primary Objective

The primary objective of this trial is to determine the efficacy of levetiracetam (LEV) versus placebo to improve executive function (NIH EXAMINER) in patients with Alzheimer's disease (AD).

2.2 Secondary Objectives

The secondary objectives of this trial are as follows:

1. To determine the efficacy of LEV versus placebo to suppress epileptiform activity in those who have epileptiform activity on their baseline M/EEGs.
2. To determine the efficacy of LEV versus placebo to improve cognitive function for the following tasks:
 - a. Stroop interference naming (number correct), and
 - b. Alzheimer's Disease Assessment Scale-cognitive subscale (ADAS-cog).
3. To determine the effects of LEV versus placebo on degree of disability and behavior using the following measures:
 - a. Clinical Dementia Rating-Sum of Boxes (CDR-SOB),
 - b. Alzheimer's Disease Cooperative Study-Activities of Daily Living Scale (ADCS-ADL),
 - c. ADCS-clinical global impression of change (ADCS-CGIC), and
 - d. neuropsychiatric inventory (NPI).

2.3 Exploratory Objectives

The exploratory objectives of this trial for patients with AD and seizures or epileptiform activity are as follows:

1. To explore the effects of LEV versus placebo on learning and memory using a computerized Virtual Route Learning Test.
2. To explore the effects of LEV versus placebo on the following outcomes measures:
 - a. Stroop color naming correct,
 - b. Stroop color naming errors (uncorrected and self-corrected),
 - c. Stroop interference naming errors (uncorrected and self-corrected), and
 - d. subcomponents of the ADAS-cog (learning and memory, language, constructional praxis, ideational praxis, and orientation).
3. To explore the effects of LEV versus placebo on clinical fluctuations using two standardized

scales (Walker et al. 2000):

- a. Clinician Assessment of Fluctuation, and
- b. One Day Fluctuation Assessment.

4. To explore the effect of LEV versus placebo on the following MEG power spectrum measures during rest and neural activity during cognitive stimulation:

- a. Delta band activity
- b. Theta band activity
- c. Alpha band activity
- d. Beta band activity
- e. Gamma band activity

5. To explore the effect of LEV versus placebo on the following magnetoencephalographic-imaging (MEG-I) functional connectivity measures in brain regions that correlate with performance on the following tasks:

- a. NIH EXAMINER composite score
- b. NIH EXAMINER – antisaccade
- c. NIH EXAMINER – set shifting
- d. NIH EXAMINER – flanker task
- e. NIH EXAMINER – dot counting
- f. NIH EXAMINER – spatial 1-back
- g. NIH EXAMINER – category fluency
- h. NIH EXAMINER – letter fluency
- i. ADAS-cog composite score
- j. ADAS-cog learning and memory
- k. ADAS-cog language
- l. ADAS-cog constructional praxis (visuospatial measure)
- m. ADAS-cog ideational praxis
- n. ADAS-cog orientation
- o. ADAS-cog 45-min word recall
- p. Stroop color naming correct
- q. Stroop color naming errors (uncorrected and self-corrected)
- r. Stroop interference naming correct
- s. Stroop interference naming errors (uncorrected and self-corrected)
- t. Virtual Route Learning Test
- u. Virtual Route 4-hour recall
- v. Clinician Assessment of Fluctuation
- w. One Day Fluctuation Assessment
- x. CDR-SOB
- y. ADCS-ADL
- z. ADCS-CGI
- aa. NPI

[figure not shown]
6. To explore the effect of LEV versus placebo on serum prolactin levels.

7. To explore the effects of LEV versus placebo on all primary, secondary, and exploratory measures listed above in the following subgroups:

- a. AD subjects with clinical signs of neuronal hyperexcitability including one or more of the following:
 - a. One or more unprovoked seizures within 5 years of screening,
 - b. Epileptiform activity within 5 years of screening,
 - c. Epileptiform activity on their initial overnight EEG or M/EEG, or
 - d. Epileptiform activity on either of their baseline M/EEGs (study days 1 and 57)
- b. AD subjects without clinical signs of neuronal hyperexcitability listed in (a)
- c. Early-onset AD (symptom onset < 65 years of age)
- d. Late-onset AD (symptom onset \geq 65 years of age)
- e. AD with predominant language impairment (AD-language) (Gorno-Tempini et al. 2011)
- f. AD with predominant posterior cortical atrophy (AD-PCA) (Mendez et al. 2002)
- g. AD patients not classified as AD-language or AD-PCA
- h. Very mild AD (MMSE of 24 and above)
- i. Mild to moderate AD (MMSE of 18 to 23)
- j. Subjects taking memantine
- k. Subjects not taking memantine
- l. Carriers the apolipoprotein E4 allele (obtained through umbrella projects)
- m. Noncarriers the apolipoprotein E4 allele.

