- i. Other: Fatigue, pain, decreased bone mineral density

2. Rare but Serious Side Effects

- a. Dermatologic: Stevens-Johnson syndrome, toxic epidermal necrolysis due to drug
- b. Hematologic: Pancytopenia, thrombocytopenia
- c. Hepatic: Liver failure
- d. Psychiatric: Suicidal thoughts or intent, suicide

Rationale: In preclinical investigations, we screened numerous FDA-approved AEDs in J20-hAPP mice (AD mouse model). LEV emerged as the only AED that effectively blocked epileptiform activity. LEV also improved hAPP/A β -induced network, synaptic, cognitive and behavioral dysfunction (Sanchez et al. 2012). Therapeutic blood levels of LEV in the mice were 4 μ g/ml, the exact levels that were achieved with low dosing of LEV (125 mg b.i.d) in a clinical trial for people with amnestic mild cognitive impairment (aMCI) (Bakker et al. 2012). LEV suppressed task-based hippocampal hyperactivity and modestly improved performance in a hippocampus-dependent pattern separation task in these aMCI patients, but did not improve other neuropsychological measures (Bakker et al. 2012) Whether task-based hippocampal hyperactivity and resting-state epileptic activity are related phenomena in AD patients, is unknown. Levetiracetam is well tolerated and effective as a monotherapy at suppressing seizures in patients with Alzheimer's disease and seizure disorders, often at low doses (Cumbo and Ligorri

2010, Vossel et al. 2013). No cognitive side effects were noted in AD patients with seizures taking LEV (Cumbo and Ligori 2010). Based on the above evidence, we have a strong indication to evaluate the efficacy of LEV improve cognitive function in AD. We will explore whether AD subjects with seizures or epileptiform activity, and whether AD subjects with early-onset disease who have a higher risk for epilepsy, respond better to LEV than AD subjects without these biomarkers of neuronal hyperexcitability. AD subjects without these clinical signs of neuronal hyperexcitability are also included in this study because they could have aberrant neuronal activity that is below the level of detection of surface EEG and M/EEG, and they could also respond favorably to LEV.

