9. ASSESSMENT OF EFFICACY

The efficacy endpoints for this trial include changes in epileptiform activity, cognition, degree of disability, and behavior. The exploratory endpoints for this trial include changes in cognition (novel tasks and subcomponents of established standardized tasks), clinical fluctuations, MEG power spectrum, MEG-I functional connectivity, blood prolactin levels, and subgroup analysis of all efficacy measures.

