10. STATISTICS

10.1 Sample Size Considerations

We based sample-size estimates on our hypotheses that LEV will improve cognitive performance to an extent that is clinically meaningful, compared to placebo. Standard sample-size calculations for repeated measures analysis of variance (ANOVA) (Cohen 1988) show that F tests could detect an effect size of 0.356 with power greater than 0.8 with our sample sizes, allowing for a 10% dropout rate.

For the M/EEG exams, if we observe epileptiform activity in 12 of our subjects (33%), as predicted by our preliminary data, we should be powered to detect small reductions in epileptiform activity during LEV treatment compared to placebo. As a reference, 10 hAPP mice provided robust power to detect a 40% reduction ($p<0.0005$) in spike frequency with chronic LEV administration compared to baseline (Sanchez et al. 2012).

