10.2 Statistical Analysis of Efficacy Data

Data from all subjects who complete at least the first 4 weeks of the study drug (placebo or active) will be included in the efficacy analysis. Subjects whose biomarkers (CSF or amyloid PET) are found to be unsupportive of AD after they enroll in the trial will be excluded from the efficacy analysis.

Cognitive, behavioral and functional measures, as well as M/EEG epileptiform activity, power spectral density for different frequency bands, neural activity during cognitive tasks, and MEG-I functional connectivity at study days 1, 29, 57, and 85 will be recorded and summarized. Descriptive statistics will be generated as appropriate (i.e., mean, median, range, and standard deviation for continuous data and frequency for categorical data).

Each treatment effect will be tested for the assumption of normality. If the data are not normally distributed, we will investigate transforming data so they are normally distributed or nonparametric options. If we choose parametric tests, significance testing will be performed using ANOVA for repeated measures with drug treatment (LEV or placebo) as the independent variable. Prior to this analysis, ANOVA will be used to analyze the effect of drug-placebo sequence and to compare group demographics and severity of dementia at baseline (MMSE and CDR-SOB); if any of these factors confound the relationship between the study drug and the outcome measure, then they will be included as covariates in the ANOVA model. If factors arise that limit the appropriateness of the repeated-measures ANOVA model, such as a large dropout rate or varying data collection time points causing imbalance of longitudinal data, we will substitute a linear mixed effects regression model to better fit the longitudinal data without the intrinsic constraints of the repeated-measures ANOVA framework (Fitzmaurice et al. 2004, Finucane et al. 2007). If a drug carryover effect is observed on an outcome measure between weeks 4 and 8, then we will analyze the initial 4 weeks of the study separately for this outcome measure. Analyses will be two-tailed except for analysis of epileptiform activity, which will be one-tailed based on our expectation that LEV will reduce

epileptiform activity (Sanchez et al. 2012, Mintz et al. 2009). For all analyses, the null hypotheses will be rejected at $p < 0.05$.

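### The protocol asks who responds better to LEV, but its subgroup plan contains no treatment-by-subgroup contrast to answer that

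*Combined protocol and SAP*

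**What the plan says.** The rationale in Section 1.2 poses a comparative question: do subjects with seizures or epileptiform activity, and those with early-onset disease, "respond better to LEV than AD subjects without these biomarkers of neuronal hyperexcitability"?

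The matching objective, Section 2.3 item 7, is not comparative. It reads "To explore the effects of LEV versus placebo on all primary, secondary, and exploratory measures listed above in the following subgroups" and lists thirteen subgroups. Items 7a and 7b are subjects with and without clinical signs of hyperexcitability; 7c and 7d are early and late onset, split at age 65.

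Section 9 names "subgroup analysis of all efficacy measures" among the exploratory endpoints and gives no method. Section 10.2 has no subgroup paragraph. Its general rule is that "significance testing will be performed using ANOVA for repeated measures with drug treatment (LEV or placebo) as the independent variable". Sequence, demographics and baseline severity enter as covariates only if they confound, and a linear mixed model is the fallback for dropout or imbalance. The rejection level is 0.05 for every analysis. The same section promises that "Descriptive statistics will be generated as appropriate (i.e., mean, median, range, and standard deviation for continuous data and frequency for categorical data").

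**The concern.** Whether one group responds better than another is a question about a difference between two treatment effects. The plan specifies effects of LEV against placebo and stops there. If each subgroup is analysed alone and judged at 0.05, the natural summary is that one group responded and the other did not. In a trial of 36 subjects that pattern arises often when the two true effects are identical. The trial could then report a selective benefit in hyperexcitable or early-onset patients that its data do not show, or overlook a real difference because both subgroup tests failed.

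What is at stake is the interpretation of an exploratory objective. It is, however, the objective meant to show which patients benefit.

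**Working it through.** **Inputs from the documents.** 36 subjects in a two-sequence crossover (Section 3). Section 10.1 plans for an effect size of 0.356 with power above 0.8, "allowing for a 10% dropout rate": 36 × 0.9 = 32.4, taken here as 32 completers. It also says "if we observe epileptiform activity in 12 of our subjects (33%), as predicted by our preliminary data". Tests of NIH EXAMINER are two-sided at 0.05 (Section 10.2).

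**Assumptions.** The documents give no subgroup sizes. One-third/two-thirds follows the 12 of 36, but item 7a is broader than M/EEG activity alone, so its share may be larger. No onset-age share is given, so an equal split is also shown. The unit is the SD of the within-subject LEV-minus-placebo difference; d_z is the effect in that unit, with a common SD and no period effect.

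**The plan's own figure.** Read 0.356 as Cohen's f with zero within-subject correlation (the protocol states neither). The noncentrality is then 2n × 0.356² with 1 and n − 1 degrees of freedom. Power is 0.801 at n = 33 and 0.788 at n = 32, so the stated figure reproduces up to rounding of 32.4. On that reading d_z = 0.356 × √2 = 0.503, which is why 0.50 is used below.

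**Step 1: equal true effect, separate tests.** Power in a subgroup of size n comes from the noncentral t distribution with n − 1 df and noncentrality d_z√n. The chance that exactly one of two is significant is p₁(1 − p₂) + p₂(1 − p₁). For 11/21 this is 0.323 × 0.413 + 0.587 × 0.677 = 0.531.

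| Split | Power in each, d_z 0.50 | Exactly one significant, d_z 0.50 | Same, d_z 0.40 / 0.60 |
|---|---|---|---|
| 11/21 (dropout) | 0.323, 0.587 | 0.531 | 0.453 / 0.531 |
| 16/16 (dropout) | 0.465, 0.465 | 0.498 | 0.437 / 0.475 |
| 12/24 | 0.353, 0.650 | 0.544 | 0.483 / 0.515 |
| 18/18 | 0.516, 0.516 | 0.499 | 0.461 / 0.442 |

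**Step 2: the contrast.** This is a two-sample t test on the within-subject differences with n₁ + n₂ − 2 df. The 95% half-width is t₀.₉₇₅ × √(1/n₁ + 1/n₂). For 11/21 it is 2.042 × 0.372 = 0.760.

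| Split | Power for a 0.50 SD difference | 95% CI half-width (SD) | Difference for 80% power (SD) |
|---|---|---|---|
| 11/21 | 0.255 | 0.760 | 1.08 |
| 16/16 | 0.278 | 0.722 | 1.02 |
| 12/24 | 0.280 | 0.719 | 1.02 |
| 18/18 | 0.308 | 0.677 | 0.96 |

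For two contrasts on one endpoint, the chance of at least one false positive is at most about 10% (1 − 0.95² = 0.0975 if independent).

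**Step 3: why period matters.** Section 5.2 randomises in fours and states no stratification by subgroup. Take 11 subgroup members among 32 subjects, 16 per sequence. If k of the 11 receive LEV first, the LEV-first proportions differ by k/11 − (16 − k)/21. Only k = 5 and k = 6 keep the gap below 20 points (6.9 points each), with hypergeometric probability 0.271 each. A gap of at least 20 points therefore occurs in 1 − 2 × 0.271 = 46% of allocations. If scores change by π from period 1 to period 2, LEV-first subjects' differences shift by −π and placebo-first subjects' by +π. The contrast then shifts by 2π times the gap, or 0.42π at 20.8 points (k = 4 or 7).

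**Step 4: subgroup definitions.** Item 7a can be met by epileptiform activity on the day 57 M/EEG, which follows the first treatment period. The day 1 M/EEG precedes the first dose (Section 6.3). Separately, Section 1.2 sets early-onset subjects against subjects lacking the biomarkers, whereas 7c/7d sets early against late onset. A late-onset subject may have epileptiform activity, so these are not the same comparison.

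**The case against.** The subgroup work is labelled exploratory, and no confirmatory claim rests on it. No sentence says that subgroup p-values will be compared to decide who responds better. The 50 to 54% figure is a hazard only if someone does that, and the splits behind it are assumed. All of this stands and keeps the point small, although Section 10.2 does apply the 0.05 rule to all analyses.

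A reader might infer that the plan makes an interval for the contrast impossible. It does not. Each pair of subgroups is disjoint, so two separate ANOVAs would give two effects with standard errors, from which an approximate interval follows. The information would exist; the plan simply does not call for the contrast.

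A reader might also infer that all other subgroup analyses should become descriptive. Nothing in this point requires that.

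The contrast is imprecise, and by itself will rarely settle the question. That is true, but separate subgroup tests rest on the same data and conceal the imprecision.

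Finally, the lead-in to Section 2.3, "The exploratory objectives of this trial for patients with AD and seizures or epileptiform activity are as follows", would leave 7b empty if taken literally. The synopsis gives the exploratory endpoints for patients with AD generally. This is wording to tidy, and the point does not depend on it.

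**Conclusion.** The point holds as a low-cost improvement to an exploratory analysis. The protocol states a comparative question and plans no comparative analysis. That the subgroups would be analysed separately is an inference from Sections 2.3, 9 and 10.2 taken together. With equal true effects of 0.50 SD, separate tests would disagree in about 50 to 54% of trials (44 to 54% for effects of 0.40 to 0.60), given the assumed splits, a paired analysis and a common SD.

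The documents do not support the stronger readings that the trial has committed to comparing p-values, that no interval could be obtained, or that the primary or secondary results are compromised.

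**What to change.** Add a short paragraph to Section 10.2:

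- For 7a/7b and 7c/7d, on NIH EXAMINER, add a treatment-by-subgroup term to the repeated-measures ANOVA or its mixed-model fallback, with period in the model.
- Report the between-subgroup difference in LEV effect with its 95% confidence interval, labelled as the exploratory answer to the question in Section 1.2.
- For this contrast, define hyperexcitability status from information available by study day 1, or keep 7a as written and show the day 1 version as a sensitivity analysis.
- State that 7c/7d compares early with late onset, which differs from the comparator in Section 1.2.
- State that power is low, so that a non-significant interaction is not evidence of equal response.

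Leave the other objective 7 analyses as planned.

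The cost is one paragraph, with no new data or visits. The day 1 definition may move some subjects from 7a to 7b; the documents do not allow the number to be estimated. The interval will span about ±0.7 to 0.8 SD, and the test would miss a true 0.50 SD difference in about 70 to 75% of trials.

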3. STUDY DESIGN

This is a phase 2a, single-center, randomized, double-blinded, placebo-controlled, crossover study of the efficacy of LEV in patients with AD. We will enroll 36 subjects. Each subject will undergo a screening assessment, including a neuropsychological battery, caregiver interview, an overnight video-EEG including hyperventilation, a 1-hr magnetoencephalography with simultaneous EEG (M/EEG) including hyperventilation, and blood test. For patients with known seizures or subclinical epileptiform activity, the video-EEG and M/EEG will be optional. Cerebrospinal fluid (CSF) will be obtained to assess beta-amyloid ($A\beta$) peptide and tau protein levels in subjects in whom positron emission tomography (PET) amyloid imaging is not already completed or scheduled. Subjects who are consented to enroll in the treatment trial will be randomized into two groups and treated in a double-blinded design. One group will receive low-dose LEV treatment (125 mg b.i.d.) for 4 weeks, followed by washout for 4 weeks, and then placebo treatment (b.i.d) for 4 weeks, while the other group will receive these treatments in reverse sequence. At weeks 0, 4, 8, and 12, participants will undergo a 1-hr M/EEG including hyperventilation, a neuropsychological battery and caregiver interview, and serum LEV and prolactin levels.

4. ELIGIBILITY CRITERIA

4.1 Inclusion Criteria

A subject may be included in this study if he or she meets **all** of the following criteria:

1. Ability to obtain written informed consent from the patient or caregiver as a surrogate;
2. Meets National Institute on Aging-Alzheimer's Association Workgroups criteria for probable AD dementia (McKhann et al. 2011);
3. Age \leq 80 years at time of screening;
4. Willing and able caregiver who has daily contact with the subject;
5. Mini-Mental State Examination (MMSE) score \geq 18 and/or Clinical Dementia Rating (CDR) < 2 at the initial screening assessment;
6. Subjects and caregivers must be able to comply with prescribed regimen of study treatment throughout the course of the study, and meet the required time commitment of four days of in-person visits;
7. Any concurrent FDA-approved treatment for AD (such as donepezil, galantamine, or rivastigmine, and memantine) must be stable for at least 30 days prior to screening and at least 60 days prior to study day 1. Other medications (except those listed under exclusion criteria) are allowed as long as the dose is stable for 30 days prior to screening.

4.2 Exclusion Criteria

A subject will be excluded from this study if he or she meets **any** of the following criteria:

1. Any conditions that could account for cognitive deficits in addition to AD, including but not limited to Vitamin B12 or folate deficiency, abnormal thyroid function, posttraumatic conditions, syphilis, multiple sclerosis or another neuroinflammatory disorder, Parkinson's disease, vascular or multi-infarct dementia, Huntington's disease, normal pressure hydrocephalus, CNS tumor, progressive supranuclear palsy, subdural hematoma, etc.;
2. Previous history of a seizure disorder, excepting cases where the first seizure or detection of epileptiform activity was within 5 years of screening and the patient is not prescribed an anticonvulsant;
3. Significant systemic medical illnesses;
4. Use of medications likely to affect CNS functions (e.g. benzodiazepines, narcotics);

5. Severe renal dysfunction with creatinine clearance < 30 ml/min, which would affect serum LEV levels;
6. Any other medical condition which is determined by the investigators to potentially create an undue risk for an adverse effect;
7. Prior biomarker evidence unsupportive of a diagnosis of AD;
8. Participation in another AD clinical trial within 3 months of screening, or any AD clinical trial, such as a vaccine, that has potential long-term effects;
9. Treatment with another study drug or investigational drug within 30 days of screening;
10. Pregnant or lactating.

4.3 Withdrawal of Subjects

A subject may choose to withdraw from this study at any time for any reason without penalty of jeopardizing their health care or loss of benefits to which the subject is otherwise entitled.

A subject will be withdrawn from this study if one or more of the following events occur:

1. Subject requests to be withdrawn from study;
2. AE that in the judgment of the Investigator poses unacceptable risk to the subject;
3. Intercurrent illness, including seizure, that requires treatment that is not consistent with the protocol requirements, or intercurrent illness or the associated treatment that in the judgment of the Investigator poses a significant risk to the subject for continued participation in the study;
4. Pregnant or suspected of being pregnant;
5. Use of prohibited medication (listed in Section 5.7) that in the judgment of the Investigator will interfere with the interpretation of the results of this study;
6. Significant protocol violation or noncompliance on the part of the subject or the Investigator;
7. Investigator terminates the study;
8. Any other reason that in the judgment of Investigator poses unacceptable risk to the subject.

If a subject is withdrawn from the study, the date and reason will be recorded in the source documents, and final study visit evaluations will be performed if feasible. Any subject withdrawn due to a suspected study drug-related adverse event (AE) would be followed until resolution or

stabilization of the event.

If subject becomes pregnant or is suspected of being pregnant, study drug will be discontinued immediately, and the subject will be referred to an obstetrician/gynecologist experienced in reproductive toxicity for further evaluation and counseling. The subject will be followed until delivery or other termination of pregnancy for outcome.

Subjects may choose to withdraw authorization to use and disclose their Protected Health Information (PHI) as defined by the Health Insurance Portability and Accountability Act (HIPAA) of 1996 or foreign equivalent where appropriate. Such withdrawal of authorization must be made to the Investigator in writing. Any PHI collected by the Investigator prior to the date of such withdrawal will continue to be used and disclosed.

